1.4.2.4. Safety Results Describing the Combined Q2W and QW Datasets

A total of 69 subjects received at least a single dose of either EFX (52 subjects) or placebo (17 subjects) and were included in the safety analysis set. Of these, 55 subjects (EFX group: 43 [82.7%]; placebo group: 12 [70.6%]) had \geq 1 AE during the study.

Of the patients who received the 70 mg SC dose or less (the highest dose proposed in Protocol AK-US-001-0101), 3 AEs of Grade 3 or above were observed and considered not related to investigational product: two instances of transient hyperglycemia in one subject (7 mg QW dose), and one instance of transient diarrhea (7 mg QW dose).

Six subjects (8.7%) discontinued investigational product; one subject in cohort 2, four subjects in cohort 8, and one subject in the placebo group. All six subjects discontinued investigational product because of AEs. Four of the patients who discontinued were in the 140 mg QW group. The reasons for discontinuation by each of the four subjects dosed at 140 mg QW were diarrhea; vomiting; tremor; and tremor/nausea, respectively. The remaining two discontinuations (one following treatment with 7mg QW; one on placebo) were attributed by the investigator to hyperglycemia and were considered unrelated to investigational product. Subjects were washed off anti-diabetic medications two weeks prior to the first dose and remained so until end of study. A summary of the treatment-related AEs and withdrawals is provided in Table 2.

There were no trends indicative of clinically important treatment-related laboratory abnormalities. No trends in clinically significant abnormalities in vital signs and ECG were noted in subjects treated with EFX or placebo. At the end of study visit (EOS), 7 subjects (13.5%) tested positive for anti-EFX binding, non-neutralizing antibodies dosing with EFX. Three of these 7 subjects returned for a follow-up antibody sample collected at least 2 months after the End of Study (EOS) visit. All 3 subjects tested negative for anti-EFX antibodies.

		EFX							
	Placebo	QW				Q2W			
	QW/Q2W (N=17)	7 mg (N=7)	21 mg (N=6)	70 mg (N=6)	140 mg (N=9)	7 mg (N=6)	21 mg (N=6)	70 mg (N=6)	140 mg (N=6)
Subjects reporting all- grade IP-related TEAEs (n)	3	2	4	5	8	3	3	2	3
Grade 2-4*	0	0	1	0	2	0	1	0	1
Adverse events with two or more observations									
Nausea (all grade)	0	1	3	0	6	0	2	1	2
Grade 2-4	0	0	0	0	0	0	0	0	2
Diarrhea (all grade)	1	1	0	2	2	0	1	1	1
Grade 2-4	0	0	0	0	0	0	1	0	0

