- i Refer to Table 3. At visits where CTX-1 or lipids are collected, the samples to be collected in the morning following an overnight fast of at least 8 hours.
- j PK sampling will be obtained pre-dose at all timepoints listed and at 48-96 hours post-dose on weeks 4 and 8 to correspond to C_{max}.
- k Samples will be obtained for detection of ADA against EFX and if required a neutralizing ADA assay will be run on the same sample.
- 1 Pre-baseline labs should be collected 4 weeks post-Screening.
- m Saliva cortisol testing will be obtained pre-dose at all timepoints listed and at 48 96 hours post-dose on Weeks 4 and 8 to correspond to C_{max}.
- n For female subjects of childbearing potential only. Serum pregnancy test at screening and urine pregnancy test at other time points.
- o At the discretion of the Investigator.

- Serum storage samples banked for possible additional clinical testing.
- q At least 2-3 hours fasting is required prior to all elastography assessments.
- r DXA scan should include lumbar spine, femoral neck, and total hip with Subjects in the standard (supine) position. Total body composition may also be collected at the DXA timepoints, where available, to determine body fat distribution.
- s All subjects will receive counseling regarding lifestyle modifications including the maintenance of a healthy diet and participation in regular exercise at the Baseline Visit. At each subsequent visit, subjects will be asked if there has been a significant change in diet, or physical activity.
- t Endogenous FGF21 serum sample to be collected in the morning following an overnight fast of at least 8 hours.
- u Weight, waist and hip circumference should be obtained by the same study personnel between visits for each subject to minimize variability in the measurement. On dosing days, weight will be collected pre-dose. Weight should be obtained using a calibrated scale. The subject should be weighed in consistent clothing.
- v Only confirmatory ALT/AST to be collected at the Pre-Baseline Visit to confirm eligibility. Pre-Baseline labs may not be repeated if inclusion criteria is not met.
- w Administration of study drug should occur following all other study procedures and sample collection for that visit.
- x Glucose only to be measured. Sample should be collected at the end of the study visit.
- y HbA1c only to be measured.

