### 3.5.2 Clinical Laboratory Tests

Chemistry, hematology, and coagulation samples will be collected at Screening, Pre-Baseline, Baseline (Day 1), Week 1, Week 4, Week 8, Week 12, Week 16 and Week 20 Safety follow-up.

All continuous laboratory parameters except of liver injury and function markers (see section 2.3.3) will be summarized descriptively by value at baseline and each planned post-baseline visit, together with the corresponding changes from baseline. All categorical laboratory parameters will be tabulated at baseline and each planned post-baseline visit.

For the selected parameters, the incidence of graded treatment-emergent laboratory abnormalities will be presented for laboratory data using the grading scheme in the Common Terminology Criteria for Adverse Events (CTCAE) Version 5.0.

Laboratory	CTCAE Term	Grade 1	Grade 2	Grade 3	Grade 4
Chemistry	Alanine aminotransferase increased	>ULN - 3.0 x ULN if baseline was normal;	>3.0 - 5.0 x ULN if baseline was normal;	>5.0 - 20.0 x ULN if baseline was normal;	>20.0 x ULN if baseline was normal;
		1.5 - 3.0 x baseline if baseline was abnormal	>3.0 - 5.0 x baseline if baseline was abnormal	>5.0 - 20.0 x baseline if baseline was abnormal	>20.0 x baseline if baseline was abnormal
	Aspartate aminotransferase increased	>ULN - 3.0 x ULN if baseline was normal;	>3.0 - 5.0 x ULN if baseline was normal;	>5.0 - 20.0 x ULN if baseline was normal;	>20.0 x ULN if baseline was normal;
		1.5 - 3.0 x baseline if baseline was abnormal	>3.0 - 5.0 x baseline if baseline was abnormal	>5.0 - 20.0 x baseline if baseline was abnormal	>20.0 x baseline if baseline was abnormal
	Blood bilirubin increased	Total Bilirubin	Total Bilirubin	Total Bilirubin	Total Bilirubin
	incroasou	>ULN - 1.5 x ULN if	>1.5 - 3.0 x ULN if	>3.0 - 10.0 x ULN if	>10.0 x ULN if
		baseline was	baseline was	baseline was	baseline was
		normal;	normal;	normal;	normal;

Laboratory	CTCAE Term	Grade 1	Grade 2	Grade 3	Grade 4
		> 1.0 - 1.5 x baseline if baseline was abnormal	>1.5 - 3.0 x baseline if baseline was abnormal	>3.0 - 10.0 x baseline if baseline was abnormal	>10.0 x baseline if baseline was abnormal
	Alkaline phosphatase increased	>ULN - 2.5 x ULN if baseline was normal;	>2.5 - 5.0 x ULN if baseline was normal;	>5.0 - 20.0 x ULN if baseline was normal;	>20.0 x ULN if baseline was normal;

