		2.0 - 2.5 x baseline if baseline was abnormal	>2.5 - 5.0 x baseline if baseline was abnormal	>5.0 - 20.0 x baseline if baseline was abnormal	>20.0 x baseline if baseline was abnormal
	Creatinine increased	>ULN - 1.5 x ULN	>1.5 - 3.0 x baseline; >1.5 - 3.0 x ULN	>3.0 x baseline; >3.0 - 6.0 x ULN	>6.0 x ULN
	CPK increased	>ULN - 2.5 x ULN	>2.5 x ULN - 5 x ULN	>5 x ULN - 10 x ULN	>10 x ULN
	Hyperkalemia	Potassium	Potassium	Potassium	Potassium
		>ULN - 5.5 mmol/L	>5.5 - 6.0 mmol/L	>6.0 - 7.0 mmol/L	>7.0 mmol/L
	Serum amylase increased	>ULN - 1.5 x ULN	>1.5 - 2.0 x ULN	>2.0 - 5.0 x ULN	>5.0 x ULN
	Hypoglycemia	Glucose	Glucose	Glucose	Glucose
		<lln -="" 55="" dl;
<lln -="" 3.0="" l<="" mmol="" td=""><55 - 40 mg/dL; <3.0 - 2.2 mmol/L	<40 - 30 mg/dL; <2.2 - 1.7 mmol/L	<30 mg/dL; <1.7 mmol/L;	</lln></lln>	<55 - 40 mg/dL; <3.0 - 2.2 mmol/L	<40 - 30 mg/dL; <2.2 - 1.7 mmol/L	<30 mg/dL; <1.7 mmol/L;
	GGT increased	>ULN - 2.5 x ULN if baseline was normal;	>2.5 - 5.0 x ULN if baseline was normal;	>5.0 - 20.0 x ULN if baseline was normal;	>20.0 x ULN if baseline was normal;
		2.0 - 2.5 x baseline if baseline was abnormal	>2.5 - 5.0 x baseline if baseline was abnormal	>5.0 - 20.0 x baseline if baseline was abnormal	>20.0 x baseline if baseline was abnormal
Hematology	Anemia	Hemoglobin (Hgb)	Hemoglobin (Hgb)	Hemoglobin (Hgb)	
		<lln -="" 10.0="" dl;
<lln -="" 6.2="" l;
<lln -="" 100="" g="" l<="" td=""><10.0 - 8.0 g/dL; <6.2 - 4.9 mmol/L; <100 - 80 g/L	<8.0 g/dL; <4.9 mmol/L; <80 g/L		</lln></lln></lln>	<10.0 - 8.0 g/dL; <6.2 - 4.9 mmol/L; <100 - 80 g/L	<8.0 g/dL; <4.9 mmol/L; <80 g/L	
	Hemoglobin increased	Hemoglobin > ULN &	Hemoglobin > ULN &	Hemoglobin > ULN &	
		Increase in >0 - 2 g/dL	Increase in >2 - 4 g/dL	Increase in >4 g/dL	
	CD4 lymphocytes decreased	<lln -="" 500="" mm3;
<lln -="" 0.5="" 10e9="" l<="" td="" x=""><500 - 200/mm3; <0.5 - 0.2 x 10e9 /L	<200 - 50/mm3; <0.2 x 0.05 - 10e9 /L	<50/mm3; <0.05 x 10e9 /L	</lln></lln>	<500 - 200/mm3; <0.5 - 0.2 x 10e9 /L	<200 - 50/mm3; <0.2 x 0.05 - 10e9 /L	<50/mm3; <0.05 x 10e9 /L

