	Neutrophil count decreased	<lln -="" 1500="" mm3;
<lln -="" 1.5="" 10e9="" l<="" td="" x=""><1500 - 1000/mm3; <1.5 - 1.0 x 10e9 /L	<1000 - 500/mm3; <1.0 - 0.5 x 10e9 /L	<500/mm3; <0.5 x 10e9 /L	</lln></lln>	<1500 - 1000/mm3; <1.5 - 1.0 x 10e9 /L	<1000 - 500/mm3; <1.0 - 0.5 x 10e9 /L	<500/mm3; <0.5 x 10e9 /L
	White blood cell decreased	<lln -="" 3000="" mm3;
<lln -="" 10e9="" 3.0="" l<="" td="" x=""><3000 - 2000/mm3; <3.0 - 2.0 x 10e9 /L	<2000 - 1000/mm3; <2.0 - 1.0 x 10e9 /L	<1000/mm3; <1.0 x 10e9 /L	</lln></lln>	<3000 - 2000/mm3; <3.0 - 2.0 x 10e9 /L	<2000 - 1000/mm3; <2.0 - 1.0 x 10e9 /L	<1000/mm3; <1.0 x 10e9 /L
	Platelet count decreased	<lln -="" 75,000="" mm3;
<lln -="" 10e9
/L</lln></lln>	<75,000 - 50,000/mm3; <75.0 - 50.0 x 10e9 /L	<50,000 - 25,000/mm3; <50.0 - 25.0 x 10e9 /L	<25,000/mm3; <25.0 x 10e9 /L
Coagulation	INR increased	>1.2 - 1.5;	>1.5 - 2.5;	>2.5;	
		>1 - 1.5 x baseline if on anticoagulation	>1.5 - 2.5 x baseline if on anticoagulation	>2.5 x baseline if on anticoagulation	
		•	•	•	•

For the other parameters, the incidence of abnormalities (as defined by normal ranges) prior to the first dose of study drug and after the first dose of study drug will be summarized with counts and percentages of subjects.

The incidence of treatment-emergent laboratory abnormalities, defined as values that increase at least one toxicity grade from baseline at any time post baseline up to and including the date of last dose of study drugs plus 30 days, will be summarized with counts and percentages of subjects by treatment group. If baseline data are missing, then any graded abnormality (i.e., at least a Grade 1) will be considered treatment-emergent. If no pre-treatment laboratory value is available, the baseline value will be assumed to be normal (i.e., no grade [Grade 0]) for the summary of graded laboratory abnormalities.

Evaluation of drug-induced serious hepatotoxicity (eDISH) plot will be provided to display peak serum ALT and Total Bilirubin (TB) levels for each subject. The peak serum AST versus TB levels for each subject will also be provided.

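### For laboratory parameters without a CTCAE row, the planned before/after counts do not show who became abnormal or in which direction, and on the plain reading high glucose and low potassium get no threshold count

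*SAP*

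**What the plan says.** SAP 3.5.2 uses two counting rules.

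- **Tabled parameters.** "For the selected parameters, the incidence of graded treatment-emergent laboratory abnormalities will be presented", with CTCAE version 5.0 grades. Treatment-emergent abnormalities are "defined as values that increase at least one toxicity grade from baseline at any time post baseline", up to last dose plus 30 days. Pre-existing abnormality is therefore handled for these analytes.
- **All remaining parameters.** The summary is "the incidence of abnormalities (as defined by normal ranges) prior to the first dose of study drug and after the first dose of study drug", as counts and percentages of subjects. No shift from baseline, no restriction to subjects in range at baseline and no split into high and low is mentioned.

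Within the CTCAE table, potassium has a hyperkalemia row only (Grade 1 is ">ULN - 5.5 mmol/L") and glucose a hypoglycemia row only. White cells, neutrophils and platelets are graded low only, and INR high only. Hemoglobin is graded both ways: an anemia row and a "Hemoglobin increased" row.

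SAP 3.5.2 lists sampling at "Screening, Pre-Baseline, Baseline (Day 1), Week 1, Week 4, Week 8, Week 12, Week 16 and Week 20 Safety follow-up". Protocol Appendix B, footnote v, narrows one of these visits: "Only confirmatory ALT/AST to be collected at the Pre-Baseline Visit to confirm eligibility". SAP 3.5 summarises safety data by treatment received.

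**The concern.** Safety and tolerability are the primary objective of Cohort C, so the laboratory tables are part of the main evidence. For an untabled parameter, the question is who moved out of range on treatment, and which way. The planned display cannot answer it. A subject who was out of range at entry and never changed adds to the post-dose figure. The treatment-emergent rule cannot help, because it needs a toxicity grade and these parameters have none.

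The two periods also offer different numbers of chances to be out of range, so a before/after reading shows a rise even if the drug does nothing.

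For tabled analytes the gap is one of direction. The normal-range rule is written for the parameters not in the table. Glucose and potassium are in the table, so on the plain reading neither rule counts a high glucose or a low potassium. Glucose is sampled more often than the rest of the panel (Appendix B, footnote x, adds glucose-only samples at the intermediate weekly visits), and Cohort C entry allows HbA1c up to 9.5%. Some subjects may therefore start with high glucose, which is where a shift display is most informative.

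**Working it through.** The documents give no rate, power or event count for this analysis, so there is no stated figure to reproduce. The rates below are assumptions, shown over a range.

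**1. Number of samples (Cohort C, untabled parameters).** Before first dose: Screening and Day 1, so 2, because Pre-Baseline is ALT/AST only. After first dose: Weeks 1, 4, 8, 12 and 16, so 5, or 6 with Week 20. Whether Week 20 counts depends on the safety window. Appendix B shows the last dosing visit as Week 15. Target days in SAP 3.1.2 are 106 for Week 15 and 141 for Week 20, and 141 − 106 = 35 days, beyond the 30-day limit for a subject exactly on schedule.

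**2. What the two counts can identify.** If *a* of *n* subjects are abnormal before and *b* after, the number newly abnormal lies between max(0, b − a) and min(b, n − a). For the EFX arm, n = 20:

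| Before | After | Newly abnormal |
|---|---|---|
| 8 | 8 | 0 to 8 |
| 5 | 9 | 4 to 9 |
| 10 | 12 | 2 to 10 |

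**3. Rise with no drug effect.** With per-sample out-of-range rate p and k independent samples, the chance of at least one abnormal value is 1 − (1 − p)^k.

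| Assumed p | 2 samples | 5 samples | 6 samples |
|---|---|---|---|
| 2.5% | 4.9% | 11.9% | 14.1% |
| 5% | 9.8% | 22.6% | 26.5% |
| 10% | 19.0% | 41.0% | 46.9% |

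At 5% that is about 2.0 of 20 subjects before and 4.5 to 5.3 after.

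Repeat values from one subject are correlated, which shrinks the gap. In a beta-binomial model with mean 5%, an intraclass correlation of 0.3 gives 8.3% before and 14.4% to 15.7% after. At 0.6 it is 6.9% against 9.6% to 10.1%, which is 0.5 to 0.6 of 20 subjects.

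**4. Dilution of the between-arm contrast.** Let a share c in each arm be stably abnormal from baseline, and let e (EFX) and q (placebo) be the new-abnormality rates among the rest. The planned post-dose figures are c + (1 − c)e and c + (1 − c)q, so their difference is (1 − c)(e − q). With assumed c = 30%, e = 30% and q = 5%:

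- EFX: 0.30 + 0.70 × 0.30 = 51%
- placebo: 0.30 + 0.70 × 0.05 = 33.5%
- difference: 17.5 points, against 25 points among subjects in range at baseline

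With the same e and q, c = 10% gives 0.9 × 25 = 22.5 points, and c = 50% gives 12.5.

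**The case against.** Four stronger readings are tempting, and the documents do not support them.

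- **That graded analytes are counted in one direction only.** Hemoglobin has both directions. The statement is true of most rows, including glucose and potassium.
- **That high glucose and low potassium are never seen.** Both appear in values and changes by visit, in listings, and in AE tables if recorded as AEs. Glycemic-control biomarkers such as HbA1c and HOMA-IR have their own ANCOVA and a summary by diabetes status. The SAP also does not say outright whether the ungraded direction of a tabled analyte falls under the normal-range rule, so this is a plain reading of a silent point. What remains is that visit means can hide individual excursions, listings are not summaries, and Protocol 6.21 makes out-of-range values AEs only if the investigator judges them clinically significant.
- **That unequal sampling biases EFX against placebo.** The schedule is the same in both arms and safety data are shown by arm. The pre-dose count is also displayed, so pre-existing abnormality is not hidden. The sampling problem affects the before/after reading only.
- **That earlier data show a hyperglycemia risk.** Two Phase 1b discontinuations "were attributed by the investigator to hyperglycemia and were considered unrelated to investigational product". One was on placebo and one on 7 mg QW, and subjects had been washed off antidiabetic drugs. Fasting glucose rose by up to 53% with 140 mg Q2W, but it fell by up to 34% and 32% with 70 mg and 140 mg QW, and Cohort C is dosed QW. Hypoglycemia is the AESI, so grading the low side has a rationale. Diarrhea is also an AESI, but the documents do not link it to low potassium.

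Two further points stand. The dilution in step 4 is a change of denominator, and its inputs have no source. The analytes most tied to cirrhosis (platelets, INR, bilirubin, transaminases, ALP, GGT) are graded and already use the baseline-adjusted rule. Albumin is untabled, but it has an entry limit and its own ANCOVA. How often the other untabled parameters are abnormal at entry cannot be read from the documents.

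**Conclusion.** The point holds in a limited form. For untabled parameters, the two counts do not separate new from old abnormality or high from low: 8 before and 8 after among 20 subjects fits anything from 0 to 8 new cases. This follows from the counting rule and needs no assumed rate. The no-effect rise is roughly a doubling or more if samples are independent and can be under one subject in 20 if they are strongly correlated. It applies to both arms and is not evidence of a biased treatment comparison. The loss of contrast is proportional to the share abnormal at baseline, which is unknown here.

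On direction, the absence of a threshold count for high glucose and low potassium is a gap in the summary tables, to be closed by a statement in the SAP. It is not a finding that either is a safety signal.

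This is a cheap improvement. The analysis is descriptive, with about 30 subjects and no hypothesis test attached, but it serves the cohort's primary objective.

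**What to change.** In SAP 3.5.2, replace the before/after sentence with a shift table by treatment group. Rows are baseline status (low, normal, high), with baseline as defined in SAP 3.1.3. Columns are status at the worst post-baseline low and, separately, at the worst post-baseline high. Apply it to every parameter that has a normal range but no CTCAE row, and to the ungraded direction of tabled analytes, at least high glucose and low potassium. State the post-dose window, and whether Week 20 values fall inside it.

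Keep the existing treatment-emergent definition, a rise of at least one grade from baseline, for every graded direction. A blanket rule that an abnormality is treatment-emergent only if the value was in range at baseline should not be applied to graded analytes. It would give them a second definition in conflict with Protocol 7.7.3 and SAP 3.5.2, and would miss worsening in subjects already abnormal.

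The new table should still be read against placebo, because taking the worst of five or six samples will move some in-range subjects out of range by chance in both arms. The cost is a few lines of SAP text and one additional standard table shell, with no new data.

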### 3.5.3 Vital Signs

Height will be measured without shoes at Screening. Other vital signs (body weight, BMI, systolic and diastolic blood pressure, pulse, respiration rate and oral temperature) will be measured at each visit. Triplicate blood pressure and heart rate will be measured at Baseline (Day 1) and at 48 - 96 hours post-dose on Weeks 4 and Week 8.

Values and changes from baseline to each visit and timepoint for vital signs will be summarized descriptively. Triplicate measurements will be averaged prior to summary.

### 3.5.4 12-Lead Electrocardiograms

12-lead ECG will be measured at Screening, Baseline (Day 1) and Week 16.

Values and changes from baseline of ECG parameters (heart rate, PR interval, QRS Interval, QT interval, QTcB interval, QTcF interval and RR interval) and overall interpretation will be summarized by visit. The number and percentage of subjects with absolute QTc interval values in the pre-specified categories (>450, >480, and >500 msec), and QTc interval change (>30 and >60 msec) will be summarized.

### 3.5.5 Other Safety Assessments

ADA, NAb and other safety data will be listed. Additionally, the subject visits impacted by COVID-19 will be listed.

### 3.6 Pharmacokinetic (PK) Assessment

PK sampling will be obtained pre-dose at Baseline (Day 1), Week 1, Week 4, Week 8, Week 12, Week 16, Week 20 Safety follow-up, and at 48-96 hours post-dose on Week 4 and Week 8.

Plasma EFX concentrations will be listed and summarized by treatment group, visit, and time point for the PK Analysis Set.

## 3.7 Pharmacodynamic (PD) Assessment

Saliva cortisol testing will be obtained pre-dose at Baseline (Day 1), Week 1, Week 4, Week 8, Week 12, Week 16, Week 20 Safety follow-up, and at 48-96 hours post-dose on Week 4 and Week 8.

Values of Saliva cortisol and changes from baseline to each visit will be summarized descriptively on Safety Set.

ANCOVA model with treatment group as a factor and baseline value as a covariate will be used for analyzing the absolute change from baseline to Week 16. LS means, 95% confidence intervals and p-values will be presented. The analysis will be based on the ovbserved values and no adjustments for multiplicity will be made.

### 3.8 Bone Biomarker Assessment

Bone biomarkers samples (Osteocalcin, P1NP, CTX-1, BSAP, PTH, and Vitamin D) will be collected at Baseline (Day 1), Week 1, Week 4, Week 8, Week 12, Week 16 and Week 20 Safety follow-up.

Values of bone biomarkers and changes from baseline to each visit will be summarized descriptively on Safety Set.

ANCOVA model with treatment group as a factor and baseline value as a covariate will be used for analyzing the absolute change from baseline to Week 16. LS means, 95% confidence intervals and p-values will be presented. The analysis will be based on the ovbserved values and no adjustments for multiplicity will be made.

### 4 DATA MONITORING COMMITTEE (DMC)

An external DMC that consists of two hepatologists, one cardiologist and a statistician will review the progress of the study.

The DMC's specific activities will be defined by a mutually agreed charter, which will define the DMC's membership, conduct, and meeting schedule.

While the DMC will be asked to advise Akero regarding future conduct of the study, including possible early study termination based on the stopping rules from the protocol, Akero retains final decision-making authority on all aspects of the study.

